1.2.4 Rationale for the study

There is clearly an unmet need to identify improved therapies for patients with NSCLC. Anetumab ravtansine is an ADC targeting mesothelin. It was well tolerated in phase I clinical studies with the predictable toxicity profile and evidence of clinical activity. Clinical and pre-clinical data indicate that anetumab ravtansine is active in mesothelin-expressing cancers. We have described mesothelin expressing lung adenocarcinoma as a specific subgroup of NSCLC with distinct mutational characteristics. The primary objectives of this trial are to assess the safety and tolerability of anetumab ravtansine in patients with previously treated unresectable locally advanced or metastatic lung adenocarcinoma (stage IIIB or IV), and to determine a preliminary estimate of the response rate of the treatment.

2 ELIGIBILITY ASSESSMENT AND ENROLLMENT

2.1 ELIGIBILITY CRITERIA

2.1.1 Inclusion Criteria

2.1.1.1 Subjects must have histologically or cytologically confirmed previously treated unresectable mesothelin expressing advanced lung adenocarcinoma (stage IIIB or IV) as confirmed by the Laboratory of Pathology, NCI

- **2.1.1.2** Subjects must have positive mesothelin expression in the archival tumor tissue, defined as the mesothelin membrane intensity score of 2+ or 3+ (on the 0-3 scale) expressed on the membrane of $\geq 10\%$ of tumor cells.
- **2.1.1.3** Subjects must provide sample of archival tumor tissue (tissue block preferred, at least 5 formalin-fixated, paraffin-embedded [FFPE] slides acceptable) collected any time before the general screening. A fresh biopsy will be collected if archival sample is unavailable or insufficient.
- **2.1.1.4** Subjects must have measurable disease, defined as at least one lesion that can be accurately measured in at least one dimension (longest diameter to be recorded for non-nodal lesions and short axis for nodal lesions) as ≥ 20 mm with conventional techniques or as ≥ 10 mm with spiral CT scan. See Section 6.3 for the evaluation of measurable disease.
- 2.1.1.5 Subjects with resected primary tumors who have documented metastases are eligible.
- **2.1.1.6** Subjects should have received at least one prior platinum based chemotherapy and an immune checkpoint targeted agent. Subjects with epidermal growth factor receptor [EGFR]-mutated and anaplastic lymphoma kinase [ALK]-translocated NSCLC should have received FDA-approved targeted therapies as appropriate.
- 2.1.1.7 Age ≥18 years. Because no dosing or adverse event data are currently available on the use of anetumab ravtansine in subjects <18 years of age, children are excluded from this study.

- **2.1.1.8** ECOG performance status ≤ 2 (see Appendix B).
- **2.1.1.9** Subjects must have adequate bone marrow function as assessed by the following laboratory test results:
 - Hemoglobin ≥ 9.0 g/dL or ≥ 5.6 mmol/L
 - Absolute neutrophil count (ANC) \geq 1,500/mm³ or \geq 1.5 x 10⁹/L
 - Platelet count $\geq 100,000/\text{mm}^3$ or $\geq 100 \times 10^9/\text{L}$
- **2.1.1.10** Subjects must have adequate kidney function, with serum creatinine <1.5 x ULN or calculated glomerular filtration rate (GFR) of > 45/mL/min/1.73 m2
- **2.1.1.11** Subjects must have adequate liver function as assessed by the following laboratory test results:
 - Total bilirubin ≤ 1.5 times the upper limit of normal (ULN)
 - Aspartate aminotransferase (AST) and alanine aminotransferase (ALT) ≤3.0 times ULN in subjects without liver metastases or ≤5.0 times ULN in subjects with liver metastases
- **2.1.1.12** Subjects must have adequate coagulation, as assessed by the following laboratory test results:
 - INR or $PT \le 1.5 \text{ x ULN}$
 - $PTT \le 1.5 \text{ x ULN}$
- 2.1.1.13 Due to the lack of adequate reproductive toxicity data on anetumab ravtansine, subjects must use 2 forms of highly effective contraception concomitantly from the initiation of study therapy until 6 months after the last dose of study therapy. Additionally, the use of condoms is required. It should also be noted that, where 2 forms of effective

contraception are required, a subject may choose to use a double-barrier method consisting of condom and cervical occlusive cap / diaphragm with spermicide

- **2.1.1.14** Ability of subject to understand and the willingness to sign a written informed consent document.
- **2.1.1.15** Subjects must provide a signed informed consent before any screening procedures.

2.1.2 Exclusion Criteria

- **2.1.2.1** Subjects who have a previous or concurrent cancer that is distinct in primary site or histology from lung adenocarcinoma, except cervical carcinoma in situ, treated basal cell carcinoma, superficial noninvasive bladder tumors or any previous cancer curatively treated <2 years before the start of study treatment.
- 2.1.2.2 Subjects who have a history or current evidence of bleeding disorder, i.e. any hemorrhage/bleeding event of CTCAE Grade ≥2 within 4 weeks before the start of study treatment.
- **2.1.2.3** History of symptomatic metastatic brain or meningeal tumors unless the subject is > 3 months from definitive therapy and has no evidence of tumor growth on an imaging study within 2 weeks prior to study entry. Subjects with brain metastases must not be undergoing acute corticosteroid therapy or steroid taper. Chronic steroid therapy is acceptable provided that the dose is stable for one month prior to screening.
- **2.1.2.4** Subjects who have a history or current evidence of uncontrolled cardiovascular disease including but not limited to the following conditions:
 - 2.1.2.4.1 Congestive heart failure of New York Heart Association (NYHA) Class III or IV
 - 2.1.2.4.2 Unstable angina (symptoms of angina at rest) or new-onset angina within <3 months before the start of study treatment.
 - 2.1.2.4.3 Arterial thrombosis, deep vein thrombosis, or pulmonary embolism within <3 months before the start of study treatment.
 - 2.1.2.4.4 Myocardial infarction or stroke within <3 months before the start of study treatment.
 - 2.1.2.4.5 Pericarditis (any CTCAE grade), pericardial effusion (CTCAE Grade ≥2) or pleural effusion (CTCAE Grade ≥2)
 - 2.1.2.4.6 Cardiac arrhythmia requiring anti-arrhythmic therapy. Subjects receiving digoxin, calcium channel blockers except verapamil, or beta-adrenergic blockers except propranolol are eligible at the investigator's discretion if the dose has been stable for at least 2 weeks before the start of study treatment. Subjects with sinus arrhythmia and infrequent premature ventricular contractions are eligible at the investigator's discretion.
- **2.1.2.5** Subjects who have a left ventricular ejection fraction (LVEF) <50%, as assessed by echocardiogram performed at screening.
- **2.1.2.6** Subjects who have a corrected QT (QTcF) interval >480 ms (CTCAE Grade >1) determined by the electrocardiogram (ECG) recorder's algorithm on the screening ECG.

- **2.1.2.7** Subjects who have a history or current evidence of uncontrolled hypertension defined as systolic blood pressure >150 mmHg or diastolic blood pressure >95 mmHg at screening despite optimal medical management. Subjects with a history of mild to moderate hypertension are eligible at the investigator's discretion if the hypertension is adequately controlled by antihypertensive treatment used at a stable dose for at least 2 weeks before the start of study treatment.
- **2.1.2.8** Subjects who have a heart rate ≥ 100 beats per minute (bpm) or ≤ 45 bpm determined by the ECG recorder's algorithm on the screening ECG.
- **2.1.2.9** Women who are pregnant or breast-feeding. Women of reproductive potential must have a negative serum beta human chorionic gonadotropin (β -HCG) pregnancy test obtained within 7 days before the start of study treatment.
- **2.1.2.10** Subjects who have had a major surgery or significant trauma within 4 weeks before the start of study treatment.
- **2.1.2.11** Subjects who have had solid organ or bone marrow transplantation.
- **2.1.2.12** Subjects who have a history of hypersensitivity to any of the study drugs or their excipients, or a history of severe hypersensitivity to any other antigen.
- **2.1.2.13** Subjects who have a history of human immunodeficiency virus (HIV) infection or subjects who have an active hepatitis B virus (HBV) or hepatitis C virus (HCV) infection requiring treatment due to a theoretical concern that the degree of immune suppression associated with the treatment may result in progression of HIV infection. Subjects with chronic HBV or HCV infection are eligible at the investigator's discretion if the subject is considered non-infectious based on serological markers.
- **2.1.2.14** Subjects who have an active clinically serious infection of CTCAE Grade ≥ 2 .
- **2.1.2.15** Subjects with a non-healing serious wound, ulcer, or bone fracture unrelated to the primary tumor.
- **2.1.2.16** Subjects with corneal epitheliopathy or any eye disorder that may predispose the subjects to drug-induced corneal epitheliopathy, or may interfere with diagnosis of treatment-emergent corneal epitheliopathy at the discretion of the investigator in consultation with the ophthalmologist/optometrist. Low grades of superficial punctate keratitis, within the range seen in the normal population, should not lead to the exclusion of the patient
- **2.1.2.17** Subjects experiencing unresolved toxicity of previous antitumor therapy which is CTCAE Grade >1 before the start of study treatment, except for alopecia or hemoglobin \geq 9.0 g/dL or \geq 5.6 mmol/L.
- **2.1.2.18** Subjects with any clinical condition that is considered unstable or might jeopardize the safety of the subject and/or influence the subject's compliance in the study.
- **2.1.2.19** Subjects who have received systemic anticancer therapy within 3 weeks before the start of study treatment. Mitomycin C or nitrosoureas must be excluded within 6 weeks before the start of study treatment.
- **2.1.2.20** Subjects who have received radiotherapy to tumor lesions that would be chosen as target lesions (measurable disease) within 4 weeks before the start of treatment, except if there is objective evidence of progression of the lesion by RECIST 1.1 between the prior radiotherapy and the screening CT or MRI scan. Palliative radiotherapy to non-target lesions is allowed at the investigator's discretion.

- **2.1.2.21** Use of drugs that inhibit renal tubular secretion (e.g. probenecid and cimetidine) within 2 weeks before the start of study treatment.
- **2.1.2.22** Use of strong cytochrome P450 3A4 (CYP3A4) inhibitors or strong CYP3A4 inducers within 2 weeks before the start of study treatment.
- **2.1.2.23** Subjects who have previously received anetumab ravtansine.
- **2.1.2.24** Subjects who are concurrently receiving any other investigational agents.

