6.3.2 Disease Parameters

Measurable disease: Measurable lesions are defined as those that can be accurately measured in at least one dimension (longest diameter to be recorded) as ≥ 20 mm by chest x-ray, as ≥ 10 mm

with CT scan, or ≥ 10 mm with calipers by clinical exam. All tumor measurements must be recorded in millimeters (or decimal fractions of centimeters).

Malignant lymph nodes. To be considered pathologically enlarged and measurable, a lymph node must be \geq 15 mm in short axis when assessed by CT scan (CT scan slice thickness recommended to be no greater than 5 mm). At baseline and in follow-up, only the short axis will be measured and followed.

Non-measurable disease. All other lesions (or sites of disease), including small lesions (longest diameter <10 mm or pathological lymph nodes with \geq 10 to <15 mm short axis), are considered non-measurable disease. Bone lesions, leptomeningeal disease, ascites, pleural/pericardial effusions, lymphangitis cutis/pulmonitis, inflammatory breast disease, and abdominal masses (not followed by CT or MRI), are considered as non-measurable.

Note: Cystic lesions that meet the criteria for radiographically defined simple cysts should not be considered as malignant lesions (neither measurable nor non-measurable) since they are, by definition, simple cysts.

'Cystic lesions' thought to represent cystic metastases can be considered as measurable lesions, if they meet the definition of measurability described above. However, if non-cystic lesions are present in the same patient, these are preferred for selection as target lesions.

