Target lesions. All measurable lesions up to a maximum of 2 lesions per organ and 5 lesions in total, representative of all involved organs, should be identified as **target lesions** and recorded and measured at baseline. Target lesions should be selected on the basis of their size (lesions with the longest diameter), be representative of all involved organs, but in addition should be those that lend themselves to reproducible repeated measurements. It may be the case that, on occasion, the largest lesion does not lend itself to reproducible measurement in which circumstance the next largest lesion which can be measured reproducibly should be selected. A sum of the diameters (longest for non-nodal lesions, short axis for nodal lesions) for all target lesions will be calculated and reported as the baseline sum diameters. If lymph nodes are to be included in the sum, then only the short axis is added into the sum. The baseline sum diameters will be used as reference to further characterize any objective tumor regression in the measurable dimension of the disease.

Non-target lesions. All other lesions (or sites of disease) including any measurable lesions over and above the 5 target lesions should be identified as **non-target lesions** and should also be recorded at baseline. Measurements of these lesions are not required, but the presence, absence, or in rare cases unequivocal progression of each should be noted throughout follow-up.

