6.3.4 Response Criteria

6.3.4.1 Evaluation of Target Lesions

Complete Response (CR): Disappearance of all target lesions. Any pathological lymph nodes (whether target or non-target) must have reduction in short axis to <10 mm.

Partial Response (PR): At least a 30% decrease in the sum of the diameters of target lesions, taking as reference the baseline sum of diameters.

Progressive Disease (PD): At least a 20% increase in the sum of the diameters of target lesions, taking as reference the smallest sum on study (this includes the baseline sum if that is the smallest on study). In addition to the relative increase of 20%, the sum must also demonstrate an absolute increase of at least 5 mm. (Note: the appearance of one or more new lesions is also considered progressions).

Stable Disease (SD): Neither sufficient shrinkage to qualify for PR nor sufficient increase to qualify for PD, taking as reference the smallest sum of diameters while on study.

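### Two eligibility rules need correction: 2.1.2.1 as worded admits other cancers treated within 2 years and bars older ones, and 2.1.1.4 counts 10 to <15 mm nodes that 6.3.2 calls non-measurable

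*Combined protocol and SAP*

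**What the plan says.** **Other cancers.** Section 2.1.2.1 excludes patients with a previous or concurrent cancer other than lung adenocarcinoma, subject to exceptions. Three exceptions are named low-risk conditions: cervical carcinoma in situ, treated basal cell carcinoma and superficial noninvasive bladder tumors. The fourth is "any previous cancer curatively treated <2 years before the start of study treatment".

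**Measurable disease at entry.** Section 2.1.1.4 requires at least one measurable lesion. It records non-nodal lesions by longest diameter and, in its words, "short axis for nodal lesions) as ≥ 20 mm with conventional techniques or as ≥ 10 mm with spiral CT scan". It gives no separate size limit for nodes and ends with a general pointer to Section 6.3.

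**Measurable disease for response.** Under 6.3.2 a node is measurable only at or above "15 mm in short axis when assessed by CT scan". Nodes from "10 to <15 mm short axis), are considered non-measurable disease". Target lesions are drawn from "All measurable lesions up to a maximum of 2 lesions per organ and 5 lesions in total". Section 6.3.1 makes measurable disease at baseline a condition of being evaluable for objective response.

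**Design.** Section 8 sets a Simon minimax design in evaluable patients (13, then 20). It allows up to 26 evaluable patients if 5.5 mg/kg is selected and up to 20 if 6.5 mg/kg is selected. The accrual ceiling is 55, to cover about 50% screen failure and a small number of inevaluable patients.

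**The concern.** Both rules, applied as written, can enrol patients whose data do not serve the trial's endpoints.

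- **2.1.2.1.** The rule lets in recently treated second cancers and keeps out those treated earlier. Section 6.3.4.1 says that "the appearance of one or more new lesions is also considered progressions", and PFS in 6.3.6 counts death from any cause. Relapse of a recent second cancer could therefore be recorded as a new lesion, progression or death, and so be charged to the study treatment in response, PFS or OS.
- **2.1.1.4.** A patient whose only qualifying lesion is a node of, say, 12 mm short axis could meet the inclusion criterion. That patient would receive study drug but could not be scored for PR+CR, the primary phase 2 endpoint.

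**Working it through.** **1. The direction of the 2-year limit in 2.1.2.1**

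| Other cancer, curatively treated, not one of the three named types | Status as worded |
|---|---|
| 6 months before start | falls under the exception: allowed |
| 10 years before start | no exception applies: excluded |

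Three features of the text suggest that this is reversed:

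- The other three exceptions are low-risk cancers. A cancer treated within the last 2 years does not belong with them.
- Reading the last item as a separate exclusion does not rescue the sentence. Any other previous cancer is already excluded, so the 2-year limit would do nothing.
- The same section uses the less-than sign for exclusion windows (2.1.2.4.2 to 2.1.2.4.4, for example "pulmonary embolism within <3 months before the start of study treatment") and the greater-than sign where elapsed time lifts an exclusion (2.1.2.3, "unless the subject is > 3 months from definitive therapy").

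Other criteria block many very recent cases: 2.1.2.10 (major surgery within 4 weeks), 2.1.2.17 (unresolved toxicity), 2.1.2.18 (unstable conditions) and 2.1.2.19 (systemic therapy within 3 weeks, or 6 weeks for two drug types). None of them sets a window for a cancer treated, for example, 3 to 23 months earlier.

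**2. A patient whose only lesion is a 12 mm node**

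| Section | Result |
|---|---|
| 2.1.1.4 | 12 ≥ 10 mm on spiral CT: meets the criterion as worded |
| 6.3.2, lymph nodes | 12 < 15 mm: not measurable |
| 6.3.2, target lesions | none available |
| 6.3.1 | not evaluable for objective response |
| 6.3.4.3 | falls under the non-measurable table, which has no PR row |

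**3. The Simon design is not affected**

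Inputs from Section 8: p0 = 0.05, p1 = 0.25; stop if 0 of 13 respond; positive if 3 or more of 20 respond.

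- Early termination under p0: 0.95^13 = 0.513, against 51% stated. It reproduces.
- Probability of a positive result: the sum over x = 1 to 13 of P(X1 = x) × P(X2 ≥ 3 − x), with X1 ~ Bin(13, p) and X2 ~ Bin(7, p). This gives 0.074 at p = 0.05 (limit 0.10) and 0.903 at p = 0.25 (target 0.90).

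Both stages count evaluable patients, so a patient with only a 10 to <15 mm node takes no place among the 13 or 20. Correcting either rule leaves these figures as they are.

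**4. The accrual cost of the nodal conflict**

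Inputs from Section 8: ceiling 55, screen failure 50%. Expected number treated: 55 × 0.5 = 27.5.

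| | 5.5 mg/kg selected | 6.5 mg/kg selected |
|---|---|---|
| Evaluable patients needed | 26 | 20 |
| Registrations needed | 26/0.5 = 52 | 20/0.5 = 40 |
| Spare registrations | 55 − 52 = 3 | 55 − 40 = 15 |
| Spare treated patients | 27.5 − 26 = 1.5 | 27.5 − 20 = 7.5 |

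Assume that screen failures are independent, so that the number treated is Bin(55, 0.5). With k treated but inevaluable patients, the trial needs at least 26 + k or 20 + k treated:

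| k | P(26 evaluable supplied) | P(20 evaluable supplied) |
|---|---|---|
| 0 | 0.705 | 0.985 |
| 1 | 0.606 | 0.971 |
| 2 | 0.500 | 0.948 |

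**The case against.** The literal readings and the arithmetic are not in dispute. The case for treating this as minor runs as follows.

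- **The pointer to Section 6.3 largely resolves the nodal conflict.** Staff who follow it would find no target lesion to record. That is a real safeguard, but 2.1.1.4 still prints its own number and does not say that 6.3.2 prevails.
- **Inevaluable patients are already budgeted.** This is true, and replacement preserves power. The allowance averages only 1.5 treated patients if 26 are needed.
- **The accrual figures overstate the defect.** In part this stands. The 0.705 starting value comes from the ceiling and the screen-failure rate, and the defect itself costs about 0.10 per patient. If 5.5 mg/kg is selected, the six run-in patients at 6.5 mg/kg lie outside the phase 2 count, so a patient among them with only a small node costs nothing. If the trial stops at stage 1, 6 + 13 = 19 patients suffice, and 55 registrations supply 19 with probability 0.993.
- **The effect of 2.1.2.1 on the primary endpoint is limited.** Relapse of a second cancer cannot create a false response, and it does not undo a response already confirmed. The effect falls mainly on PFS and OS. Section 3.5.1 lists secondary malignancy separately from progression, but it does not address relapse of an earlier cancer. Such patients should also be uncommon among those already given platinum and checkpoint therapy.
- **Reversal is an inference.** This stands. The protocol nowhere states the intended direction.

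These points limit the size of the problem. They do not make either rule correct as written.

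**Conclusion.** Both points hold. As worded, 2.1.2.1 admits other cancers curatively treated within 2 years and excludes older ones outside the three named types, and no other section corrects this. The literal reading is certain. That the direction is reversed is a well-supported inference which only the sponsor can confirm. Sections 2.1.1.4 and 6.3.2 set different nodal limits, so a patient can qualify for treatment and yet be inevaluable for PR+CR.

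The documents give no frequency for either case, and few patients are likely to be affected. Type I error (0.074), power (0.903) and early termination (0.513) do not change. The nodal conflict matters mainly if 5.5 mg/kg is selected and stage 2 opens: each such patient in the phase 2 count then lowers the chance of full accrual within 55 registrations by about 0.10. This rests on the stated 50% screen failure and on independence between registrations, which is my assumption. The wording should be corrected, but the design does not need rework.

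**What to change.** 1. **2.1.2.1:** the sponsor should confirm the intended rule and rewrite it so that the direction of the 2-year limit cannot be misread and fits an exception for low-risk cancers. Putting the named exceptions and the time limit in separate sentences would do this.
2. **2.1.1.4:** align it with 6.3.2, that is, at least 15 mm short axis by CT for nodes and at least 10 mm by CT for non-nodal lesions. Alternatively, remove the numbers from 2.1.1.4 and refer specifically to 6.3.2.

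The cost is a two-line amendment. Sample size, decision rule and accrual ceiling stay as they are, and a very small number of candidates change eligibility status.

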2.2 SCREENING EVALUATION

Step 1: The following assessments may be performed as soon as the initial 1st line treatment cycles with platinum/pemetrexed are administered.

- NCI LP confirmation of diagnosis
- NCI LP determination of mesothelin expression
- Medical History and Physical Examination

Step 2: Once mesothelin expression and diagnosis are confirmed, then proceed with the following tests described below.

The following screening assessments will occur within 28 days prior to initiation of study therapy:

- Medical history and physical examination including vital signs
- ECOG Performance Status
- CT scan of chest, abdomen and/or pelvis and areas of known or suspected disease involvement; MRI may also be performed when appropriate
- FDG-PET scan
- Echocardiogram
- Electrocardiogram
- Viral markers HBsAg, anti-HCV, anti-HIV

The following screening assessments will occur within 21 days prior to initiation of study therapy:

- Ophthalmologic exam (within 3 weeks before start of study therapy)
 - Visual acuity (BCVA according to ETDRS, or Snellen, or Landolt C or other charts)
 - Measurement of ophthalmic pressure (IOP)
 - Dry eye test [Schirmer test]
 - Slit lamp

The following screening assessments will occur within 7 days prior to initiation of study therapy:

- CBC with differential; Acute Care Panel (sodium, potassium, chloride, bicarbonate, creatinine, glucose, urea nitrogen, eGFR); Hepatic Panel (alkaline phosphatase, ALT, AST, Total Bilirubin, Direct Bilirubin)
- PT, PTT
- Urinalysis
- β-HCG in women of childbearing potential

2.3 **REGISTRATION PROCEDURES**

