6.2.2 Genomic Data Sharing Plan

No large scale genomic data will be generated on this study.

6.3 **RESPONSE CRITERIA**

For the purposes of this study, patients should be re-evaluated for response every 6 weeks in the first 6 months, every 9 weeks until the end of year 2 and every 12 weeks thereafter. In addition to a baseline scan, confirmatory scans should also be obtained not less than 4 weeks following initial documentation of objective response.

Response and progression will be evaluated in this study using the new international criteria proposed by the revised Response Evaluation Criteria in Solid Tumors (RECIST) guideline (version 1.1)¹⁸. Changes in the largest diameter (unidimensional measurement) of the tumor lesions and the shortest diameter in the case of malignant lymph nodes are used in the RECIST criteria.

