6.3.3 Methods for Evaluation of Measurable Disease

All measurements should be taken and recorded in metric notation using a ruler or calipers. All baseline evaluations should be performed as closely as possible to the beginning of treatment and never more than 4 weeks before the beginning of the treatment.

The same method of assessment and the same technique should be used to characterize each identified and reported lesion at baseline and during follow-up. Imaging-based evaluation is preferred to evaluation by clinical examination unless the lesion(s) being followed cannot be imaged but are assessable by clinical exam.

Clinical lesions: Clinical lesions will only be considered measurable when they are superficial (e.g., skin nodules and palpable lymph nodes) and ≥ 10 mm diameter as assessed using calipers

(e.g., skin nodules). In the case of skin lesions, documentation by color photography, including a ruler to estimate the size of the lesion, is recommended.

Chest x-ray: Lesions on chest x-ray are acceptable as measurable lesions when they are clearly defined and surrounded by aerated lung. However, CT is preferable.

Conventional CT and MRI: This guideline has defined measurability of lesions on CT scan based on the assumption that CT slice thickness is 5 mm or less. If CT scans have slice thickness greater than 5 mm, the minimum size for a measurable lesion should be twice the slice thickness. MRI is also acceptable in certain situations (e.g. for body scans).

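### A non-progressing lesion irradiated just over 4 weeks before treatment can be a RECIST target lesion, so radiation shrinkage after the baseline scan can contribute to a partial response

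*Combined protocol and SAP*

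**What the plan says.** Section 2.1.2.20 excludes subjects who have had "radiotherapy to tumor lesions that would be chosen as target lesions (measurable disease) within 4 weeks before the start of treatment". It makes one exception, which concerns what the irradiated lesion has done since: "except if there is objective evidence of progression of the lesion by RECIST 1.1 between the prior radiotherapy and the screening CT or MRI scan". Progression of the irradiated lesion thus appears only as a way out of the 4-week bar.

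Section 6.3.2 defines measurable lesions by size and measurability. For target lesions it takes "All measurable lesions up to a maximum of 2 lesions per organ and 5 lesions in total", chosen by size, organ representation and reproducibility of measurement. Neither definition mentions earlier irradiation, and neither does the measurable-disease criterion in 2.1.1.4.

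On timing, section 2.2 lists the CT scan under "The following screening assessments will occur within 28 days prior to initiation of study therapy". Section 6.3.3 asks for baseline evaluations as near to treatment as possible and "never more than 4 weeks before the beginning of the treatment". Section 6.3 sets the first re-evaluation at 6 weeks.

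PR is "At least a 30% decrease in the sum of the diameters of target lesions" relative to baseline (6.3.4.1), and section 6.3 adds that "confirmatory scans should also be obtained not less than 4 weeks following initial documentation of objective response". Section 8 makes PR+CR the phase 2 endpoint of a single-arm Simon minimax design: stop if there are no responses in 13 evaluable patients, and regard the drug as worth further study if there are 3 or more in 20.

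**The concern.** The exclusion accepts that recent radiotherapy to a target lesion confuses the reading of response, and it accepts progression after radiotherapy as the answer. It applies that answer only inside 4 weeks, and it counts the 4 weeks to the wrong event for this purpose. What matters for PR is whether the lesion is still shrinking from radiation after the baseline scan. An interval of just over 4 weeks to first dose can be an interval of a day or so to the baseline scan.

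A single-arm trial has no control group in which the same shrinkage would show. The decisions also turn on very few events: one response among 13 keeps the trial open, and three among 20 make it a success. One response due to radiation would therefore carry real weight.

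**Working it through.** **Timing allowed by the text.** Radiotherapy on day -29 lies outside the 4-week bar, so no progression is required. A baseline scan on day -28 is within the limits of 2.2 and 6.3.3. The first re-evaluation at week 6 is day 42, which is 29 + 42 = 71 days, or about 10 weeks, after radiotherapy. Any radiation shrinkage after day -28 enters the percentage change used for PR. This is the permitted extreme; a scan nearer to day 1 leaves less of the shrinkage after baseline.

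**The plan's own design (section 8).** Inputs: p0 = 0.05, p1 = 0.25, n1 = 13 with a stop at 0 responses, n = 20 with success at 3 or more. Let X be the responses in the first 13 patients and Y those in the next 7.

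- Early termination at p0: 0.95^13 = 0.513. The plan states 51%, so this reproduces.
- P(go | p) = sum over x ≥ 1 of P(X = x) · P(Y ≥ 3 - x).
- At p = 0.05: 0.3512 × 0.0444 (x = 1) + 0.1109 × 0.3017 (x = 2) + 0.0245 (x ≥ 3) = 0.0156 + 0.0335 + 0.0245 = 0.0736.
- At p = 0.25: 0.903.

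Both error rates meet the stated alpha and beta of 0.10. The design itself is correctly calculated.

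**Effect of responses due to radiation.** Two inputs are assumptions, because the documents give no figure for either: f, the fraction of subjects with a non-progressing irradiated target lesion of this kind, and q, the probability that radiation alone then gives a confirmed PR. With a true drug response rate of 5%, the apparent rate is p = 0.05 + 0.95·f·q.

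| f | q = 10% | q = 25% |
|---|---|---|
| 5% | p = 0.0548, P(go) = 9.1% | p = 0.0619, P(go) = 12.0% |
| 10% | p = 0.0595, P(go) = 11.0% | p = 0.0738, P(go) = 17.6% |
| 20% | p = 0.0690, P(go) = 15.2% | p = 0.0975, P(go) = 30.3% |

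Over the same range, early termination falls from 51% to between 48% (f = 5%, q = 10%) and 26% (f = 20%, q = 25%).

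**Where alpha is passed.** P(go) reaches 0.10 at p = 0.0570. Then f·q = (0.0570 - 0.05)/0.95 = 0.0074, or about 0.7%.

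**One spurious responder taken as given, all other patients at 5%.**

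- In stage 1 the stop cannot trigger, and success needs 2 or more of the other 19: 1 - 0.95^19 - 19 × 0.05 × 0.95^18 = 1 - 0.3774 - 0.3774 = 0.245.
- In stage 2 the trial must first pass 13 unaffected patients. With X = 1, at least 1 more response is needed from the other 6; with X ≥ 2, success follows: 0.3512 × (1 - 0.95^6) + 0.1354 = 0.3512 × 0.2649 + 0.1354 = 0.228.

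**The case against.** Several limits are fair and stand.

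- Section 6.3.3 asks for the baseline scan as near to treatment as possible, so a day -28 scan is allowed but is not the instructed practice.
- PR is judged on a sum of up to 5 lesions representing all involved organs. The irradiated lesion must dominate that sum or be the only target lesion, and there must be no new lesion or progression elsewhere.
- The mechanism needs recent radiotherapy. A lesion irradiated long ago and now stable has its shrinkage in the baseline already, and it can only dilute a later percentage fall.
- Both f and q are assumed. At 5% and 10% the false-go probability is 9.1%, still below the stated alpha.
- Section 6.3 adopts RECIST 1.1 by citation. The gap is shown for the protocol's own text, not for the cited guideline.

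The length of a washout is also a matter of judgement, and the protocol did consider the issue.

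These points reduce the likelihood but do not close the gap. Confirmation at 4 weeks or more does not close it either, because shrinkage that persists will be confirmed.

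A reader might go further and infer that nearly all of the radiation effect falls inside the response window, or that most of these subjects will have had radiotherapy. The documents give no time course of radiation response and no radiotherapy history, so they support neither. Nor is 24.5% the trial's type I error: it is conditional on a spurious responder having occurred.

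**Conclusion.** The gap is real on the text. A site that follows 2.1.2.20, 2.2 and 6.3.2 exactly can enter a recently irradiated, non-progressing lesion as a target lesion and count its later radiation shrinkage toward the primary endpoint. How often this would happen cannot be read from the documents. Over the assumed range the false-go probability moves from the design's 7.4% to between 9.1% and 30.3%, so the effect runs from minor to serious. A small product of f and q, about 0.7%, is enough to pass alpha, and one actual case would matter (24.5% if in stage 1, 22.8% if in stage 2). The sample size, the stopping rule and the stated error rates are not in error. The weakness lies in how target lesions are selected. It is worth correcting as a cheap improvement, not as a fault that undermines the design.

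**What to change.** Add to the target-lesion paragraph of 6.3.2: a previously irradiated lesion may be a target lesion only if objective progression of that lesion has been documented between the radiotherapy and the screening scan; otherwise it is recorded as non-target. Cross-refer from 2.1.2.20 and 2.1.1.4, so that such a lesion cannot be a subject's only measurable lesion.

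This extends a condition that the protocol already uses. It also takes old, stable irradiated lesions out of the sum, where they would dilute a true response. A subject with another measurable lesion stays eligible and can still reach PR, since the table in 6.3.4.3 allows PR with non-target disease that persists without progressing. The 13/20 design and its decision rules do not change.

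The cost is one sentence and two cross-references, and an occasional subject with no other measurable lesion who is no longer eligible. That loss grows with the frequency of such lesions, as does the bias that it prevents.
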